#### **Exclusion Criterion**

1. Recipient with IGg3 Multiple Myeloma.

#### **Donor Criteria**

1. Able to sign written informed consent and be willing to provide donor lymphocytes.
2. Age 18 – 75 years
3. No physical contraindications to lymphocyte collection (i.e., severe atherosclerosis, auto-immune disease, cerebrovascular accident, prior malignancy less than 5 years ago other than non-melanoma skin cancer treated with surgery). Donors with severe atherosclerosis by history will receive a cardiology consult and be judged eligible on a case by case basis.
4. Negative donor infectious disease panel:
  - Hepatitis B surface antigen (HBsAg)
  - Anti-Hepatitis B core antibody (HBcAb)
  - Anti-Hepatitis C Virus antibody (HCV Ab)
  - Anti-Human Immunodeficiency Virus (HIV) antibody (HIV 1/2 type O Ab)
  - Anti-Human T cell lymphotropic Virus (HTLV) antibody (HTLV I/II Ab)
  - Rapid Plasma Reagen (RPR)
  - Cytomegalovirus antibody (CMV)
  - HCV/HIV Nucleic Acid test

Additional tests shall be performed as required to assess the possibility of transmission of other infectious or non-infectious diseases.

5. Negative serum Beta HCG test in a woman with child bearing potential (not post-menopausal for 12 months or no previous surgical sterilization) must use an effective method of contraception until at least 1 month after lymphocyte collection. Mothers should not breastfeed during the study.

### **Donor Eligibility Undetermined**

All products obtained from donors where eligibility has not been determined must be stored in quarantine until eligibility has been assessed. Products in quarantine are clearly labeled to prevent release. If product must be released prior to eligibility determination then urgent medical need must be documented. These products must be labeled "NOT EVALUATED FOR INFECTIOUS SUBSTANCES" and "WARNING: Advise patient of communicable disease risks".

### **Release of Products from Ineligible Donor**

The release of products from an ineligible donor requires the documentation of urgent medical need and the consent of the patient. Products are labeled with a "Biohazard" Label including "WARNING: Advise patient of communicable disease risks". Screening and test results must accompany the product and provided to the infusing physician in an envelope for review. These documents are to be properly disposed of after infusion to protect the privacy of the donor.

### **Ineligible Donors**

If donor is deemed to be ineligible, finding must be documented on the Donor Certificate.

An "Urgent Medical Need" order including reason for ineligibility must be provided to the laboratory.

## **5.0 Pretreatment evaluation**

The procedures and tests listed below are standard of care and are performed to determine recipient and donor eligibility.

### **A. Both recipient and donor:**

- 1) History and physical (H&P).
- 2) Albumin, total protein, calcium, glucose, BUN, creatinine, bilirubin, ALT, alkaline phosphatase, LDH, CBC with differential, PT/PTT. Serum B-HCG for female donor and recipient.

### **B. Recipient only:**

- 1) Immunodeficiency panel: Quantitative immunoglobulins, quantification of lymphocyte subsets (CD4 and CD8).
- 2) Cyclosporine or tacrolimus level as appropriate.
- 3) Disease restaging: SPEP, UPEP, serum and immunofixation electrophoresis, serum for free kappa and lambda light chain assay, Beta 2 Microglobulin, and C reactive protein.
- 4) Bone survey, Magnetic resonance imaging (MRI), or Positive Emission Tomography (PET)/Computed tomography(CT) as clinically indicated.
- 5) Bone marrow aspiration and biopsy for cytogenetics, chimerism, myeloma panel, and IgG subpanel.
- 6) Negative donor infectious disease panel:
  - Hepatitis B surface antigen (HBsAg)
  - Anti-Hepatitis B core antibody (HBcAb)
  - Anti-Hepatitis C Virus antibody (HCV Ab)
  - Anti-Human Immunodeficiency Virus (HIV) antibody (HIV 1/2 type O Ab)
  - Anti-Human T cell lymphotropic Virus (HTLV) antibody (HTLV I/II Ab)
  - Rapid Plasma Reagen (RPR)
  - Cytomegalovirus antibody (CMV)
  - HCV/HIV Nucleic Acid Test
  - West Nile Virus Nucleic Acid Test
  - Sickledex
  - T Cruzi AB

Additional tests shall be performed as required to assess the possibility of transmission of other infectious or non-infectious diseases.

**C. Donor only:**

- 1) Negative donor infectious disease panel:
  - Hepatitis B surface antigen (HBsAg)
  - Anti-Hepatitis B core antibody (HBcAb)
  - Anti-Hepatitis C Virus antibody (HCV Ab)
  - Anti-Human Immunodeficiency Virus (HIV) antibody (HIV 1/2 type O Ab)
  - Anti-Human T cell lymphotropic Virus (HTLV) antibody (HTLV I/II Ab)
  - Rapid Plasma Reagen (RPR)
  - Cytomegalovirus antibody (CMV)
  - HCV/HIV Nucleic Acid test

Additional tests shall be performed as required to assess the possibility of transmission of other infectious or non-infectious diseases.

## 6.0 Treatment Plan

### Idiotype Procurement

6.1 Recipient will undergo steady state plasmapheresis procedure to provide idiotype protein necessary to produce the vaccine. This is a standard procedure. Plasma (60-100 cc) from the plasmapheresis procedure will be sent to the MD Anderson Cancer Center GMP lab where it will be processed. The MDACC GMP lab will be responsible for producing the id-KLH conjugated vaccine according to the supplied standard operating procedure (see PDOL Appendices H and I). The vaccines will be kept in the GMP lab until requested. Alternatively vaccine can be produced using previously collected idiotype monoclonal protein collected on ongoing laboratory protocols and cryopreserved.

6.2 Donor will be vaccinated with an id-KLH vaccine 0.5 cc subcutaneously, once during weeks -8, -6, and -2 prior to donor lymphocyte collections.

The preferred site for the vaccine injection are the deltoid area (upper arm) and thigh. Sites should be alternated with each vaccine administration.

All donors will be observed in the clinic for two hours following vaccine administration. During the observation period, vital signs will be taken every 15 minutes during the first hour and then every 30 minutes during the second hour following vaccine administration.

6.3 GM-CSF 250 mcg/m^2 (dose rounded up to the nearest vial) S.C. will be given daily for four days (days 0-3) after each vaccine. All GM-CSF injections will be given in close proximity to the vaccination, as close to the exact site of injection as possible to ensure optimal recruitment of dendritic cells. The first dose of GM-CSF will be given by a nurse, and the remaining three doses will be given by the donor. Research staff will provide educational instructions regarding subcutaneous injection administration.

6.4 Recipient must meet the following criteria in order to receive the vaccine:

- Recipient to receive vaccine must be greater or equal than 3 months post allograft and with 5% or greater donor cell engraftment
- On a prednisone or prednisone equivalent dose of no more than 10 mg every other day at the time of registration, and with tacrolimus levels of <5 ng/dl or cyclosporine levels of < 100 ng/dl.
- Have no uncontrolled GVHD.

- Negative serum Beta HCG test in a woman with child bearing potential (not post-menopausal for 12 months or no previous surgical sterilization) and willing to use an effective contraceptive measure while on study.

If the recipient does not meet the above "pre-vaccine" criteria, the recipient and donor will be taken off the study. The donor will have follow-up tests and procedures performed, as described in Section 7.0.

- 6.5 On day 0 (day of lymphocyte collection) donors will undergo a steady state pheresis to obtain lymphocytes. Donor target cell dose will be to  $\geq 2 \times 10^7$  CD3+ cells /kg recipient weight. If the target dose is not reached after 3 collections, then the donor and the recipient will be taken off the study and the apheresis product will be discarded.
  - 6.6 If successful collection, on day 0:  $1 \times 10^7$  CD3+/cells per kg will be infused into the recipient. The rest of the cells will be cryopreserved in  $5 \times 10^7$  CD3+ cells /kg recipient weight aliquot. Premedication will include only acetaminophen 650 mg po (orally) and benadryl 25 mg iv once.
- NO STEROIDS ARE TO BE GIVEN PRIOR TO LYMPHOCYTE INFUSION.
- 6.7 After DLI on same day, recipient will receive id-KLH vaccine. The vaccine will be also administered on week 4 and week 8 post DLI. The recipient will receive a total of 3 vaccines.
  - 6.8 For the donor the time of active treatment will begin the day of the first vaccine and finish 30 days after donor lymphocyte collection.
  - 6.9 For the recipient the time of active treatment will begin the day of the donor lymphocyte infusion and finish 30 days after the last vaccination.
  - 6.10 Recipients will receive GM-CSF 250 mcg/m^2 (rounded up to the nearest vial) S.C.daily for four days (days 0-3) after each vaccine. All GM-CSF injections will be given in close proximity to the vaccination, as close to the exact site of injection as possible to ensure optimal recruitment of dendritic cells. The first dose of GM-CSF will be given by a nurse, and the remaining three doses will be given by the recipient. Research staff will provide educational instructions regarding subcutaneous injection administration.
  - 6.11 Donors and/or recipients: Fever and chills associated with vaccine administration and/or GM-CSF will be treated with acetaminophen and/or meperidine. The use of non-steroidal anti-inflammatory drugs and/or steroids should be avoided.
  - 6.12 Recipients should not receive steroid premeds, or high dose steroids for other indications unless approved by the Study Chair or his designee.
  - 6.13 Recipients failing to respond 6 months after the last vaccination can receive up to 3 subsequent doses of  $5 \times 10^7$  CD3+ cells/kg of the remaining cryopreserved cells, if no active GVHD is present. The additional lymphocyte infusions and follow up will be exactly like the first infusion.

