Kwak et al immunized nine patients with B cell lymphoma with autologous idotype protein. These patients received no anti-tumor therapy during the time of the study. They were either in complete remission or in a state of minimal residual disease following conventional chemotherapy. In addition, three patients with rapidly progressive recurrent lymphoma were enrolled in a separate safety study; all three required re-institution of chemotherapy shortly after enrollment, did not complete the immunization series, and were not studied further. They received intramuscular injections of 0.5 mg of Id conjugated to KLH at 0, 2, 6, 10, and 14 weeks, followed by two booster injections at 24 and 28 weeks. The KLH carrier provided a convenient internal control for immunocompetence of the patients, and all patients demonstrated both humoral and PBMC proliferative responses to the KLH protein, with the exception of one patient, who demonstrated only the latter. Seven of the nine patients demonstrated either a humoral (n=2) or a cell-mediated (n=4) anti-idiotypic immunological response, or both (n=1) (29). Toxicity was minimal in all twelve patients. All patients experienced transient local reactions characterized by mild erythema, induration, and discomfort, without skin breakdown, at the injection s. Id immunization was associated with a mild elevation (less than twice the normal value) of serum creatine phosphokinase 24 hours after immunization in an occasional case. These results demonstrate that patients with B cell lymphomas can be induced to make sustained idotype-specific immune responses by active immunization with purified autologous tumor-derived surface Ig. They show that autologous Id, made immunogenic by conjugation to KLH, can serve as an immunogen (antigen) to elicit host immunological responses.

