### 3.0 Background Drug Information

#### **3-A Id-KLH Vaccine Myeloma Immunoglobulin Idiotypic Vaccine (NSC-678327, BB IND 5779)**

Availability - Individual Myeloma immunoglobulin are obtained from each patient and individual vaccine is prepared for each patient at the **GMP Facility of MDACC**.

Idiotypic Vaccine Preparation - Idiotypic vaccines are prepared using a recipient's idiotype protein. The patient-specific protein will be isolated from the recipient's plasma (via plasmapheresis), purified by protein A or anti-Hu IgA affinity chromatography, and covalently coupled to a keyhole limpet hemocyanin (KLH) as described in **Appendix G**. The preparation of the final vaccine product (myeloma idiotype protein conjugated with KLH) will be performed by **GMP Facility of MDACC**. Each batch of patient-specific vaccines will be produced according to Good Manufacturing Practices (GMP) standards and will be tested for sterility, endotoxin contamination, and general safety, prior to its use in any patient. The final vaccine product (myeloma idiotype protein conjugated with KLH) will be manufactured (and vialled) by **the GMP Facility of MDACC**. Each patient-specific vaccine will be labeled to include the following information:

- a) myeloma immunoglobulin idiotype vaccine: patient-specific lot
- b) final volume and concentration of vaccine product
- c) KLH and patient-specific immunoglobulin subtype
- d) storage conditions
- e) fill date
- f) patient identification (first name/last initial)

Storage and Stability - The final product is available as a solution containing 1.1 mls of conjugated protein diluted in sodium chloride 0.9% (NS). The solution is contained in a 1.8 ml insert inside a sterile vial. The final solution contains 0.5 mg/ml of KLH conjugated to 0.5 mg/ml of the patient-specific immunoglobulin idiotype protein. Intact vials are stored at -20° C.

Administration - The patient (recipient) and donor will receive 3 subcutaneous injections of the patient-specific vaccine preparation containing 0.5 mg of the myeloma protein at the protocol specified timepoints. Both individuals will receive GM-CSF as an adjuvant to the vaccine preparation. GM-CSF will be administered as a subcutaneous injection at a dose of 250 mcg/m^2 (rounded up to the nearest vial)

daily for four consecutive days (day 0-day 3).

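### Section 6.2 orders 0.5 cc of vaccine for donors, which holds 0.25 mg of idiotype protein, half the 0.5 mg dose given in Section 3-A

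*Combined protocol and SAP*

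**What the plan says.** The vaccine dose appears in two places in the combined protocol and SAP.

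- **Section 3-A, Storage and Stability** describes the product: "The final solution contains 0.5 mg/ml of KLH conjugated to 0.5 mg/ml of the patient-specific immunoglobulin idiotype protein". On the fill it says: "The final product is available as a solution containing 1.1 mls of conjugated protein".
- **Section 3-A, Administration** gives one dose for both members of the pair, recipient and donor: "3 subcutaneous injections of the patient-specific vaccine preparation containing 0.5 mg of the myeloma protein".
- **Section 6.2** tells staff what to give the donor: "Donor will be vaccinated with an id-KLH vaccine 0.5 cc subcutaneously", once in each of weeks -8, -6 and -2.

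Section 6.7 schedules the recipient's three vaccinations (the day of lymphocyte infusion, week 4 and week 8) but gives neither a volume nor a mass. The background in Section 2.0 describes an earlier idiotype vaccine study in lymphoma: "They received intramuscular injections of 0.5 mg of Id conjugated to KLH".

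**The concern.** Section 3-A fixes a concentration and a mass, and together they imply a volume. Section 6.2 states a different volume. Someone preparing the injection from Section 3-A and someone giving it from Section 6.2 could differ twofold, each with the protocol in support.

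The primary objective (Section 1.0, repeated in Section 10.0) asks whether vaccinating the donor enhances the transfer of myeloma-specific immunity. The donor's antigen dose is therefore the exposure under test. If donors get 0.25 mg, a weak donor response cannot be read as a result for the 0.5 mg dose in Section 3-A. If staff follow different sections for different donors, dose varies within a trial of at most 10 treated patients, too few to separate a dose effect from variation between patients. If recipients are dosed by Section 3-A and donors by Section 6.2, the donor gets half the recipient's amount, although Section 3-A describes one dose for both.

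**Working it through.** **Inputs**

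| Quantity | Value | Source |
|---|---|---|
| Idiotype protein concentration | 0.5 mg/ml | Section 3-A, Storage and Stability |
| KLH concentration | 0.5 mg/ml | Section 3-A, Storage and Stability |
| Vial fill | 1.1 ml | Section 3-A, Storage and Stability |
| Dose of myeloma (idiotype) protein | 0.5 mg | Section 3-A, Administration |
| Injections per person | 3 | Sections 3-A, 6.2 and 6.7 |
| Donor volume | 0.5 cc (0.5 ml) | Section 6.2 |

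Throughout, mass = concentration × volume.

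**1. Section 3-A on its own terms**
- Volume needed for the stated mass: 0.5 mg ÷ 0.5 mg/ml = 1.0 ml.
- Idiotype protein in a vial: 1.1 ml × 0.5 mg/ml = 0.55 mg.
- Share of the vial used by 1.0 ml: 1.0 ÷ 1.1 = 91%.

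Section 3-A is internally consistent: one vial supplies one 1.0 ml dose with a small overfill.

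**2. Section 6.2 at the Section 3-A concentration**
- Mass delivered: 0.5 ml × 0.5 mg/ml = 0.25 mg.
- Ratio to the stated dose: 0.25 ÷ 0.5 = 50%.
- Over three injections: 3 × 0.25 = 0.75 mg, against 3 × 0.5 = 1.5 mg.
- Share of the vial used: 0.5 ÷ 1.1 = 45%, leaving 1.1 − 0.5 = 0.6 ml.

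**3. Readings that might reconcile the two**
- *The 0.5 mg is KLH plus idiotype.* 0.5 ml × (0.5 + 0.5) mg/ml = 0.5 mg, so the number matches. But Section 3-A attaches the 0.5 mg to the myeloma protein and lists KLH separately.
- *The 0.5 mg is the total over three injections.* 0.5 ÷ 3 = 0.167 mg each, and 0.167 ÷ 0.5 mg/ml = 0.33 ml, which is not 0.5 cc.
- *The 0.5 mg is the vial content.* The vial holds 0.55 mg, and the recipient's dose would then be stated nowhere in the supplied text.
- *The product is stronger than stated.* Putting 0.5 mg in 0.5 ml needs 0.5 ÷ 0.5 = 1.0 mg/ml, twice the stated concentration.

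The supplied text contains no other concentration, no concentrating step and no second injection per visit.

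**The case against.** The best case on the other side accepts the multiplication and questions what follows from it.

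- **Section 3-A never literally says per injection.** The phrase about 0.5 mg could attach to the preparation rather than to each injection. That is true of the grammar, but per injection is the natural reading of an administration paragraph, and the alternatives tried do not yield a consistent donor dose.
- **The slip may be in Section 3-A.** Because 0.5 cc holds 0.5 mg of KLH and idiotype combined, the error could be the label on the 0.5 mg rather than the volume in Section 6.2. This stands as a possibility. It still means that one section is wrong, and in idiotype terms the dose would be 0.25 mg.
- **The evidence for 1.0 cc is indirect.** The fill volume supports it without proving it. The lymphoma precedent is weaker: those were intramuscular injections of the patients' own idiotype, not subcutaneous vaccination of a healthy donor with another person's protein. Moving to 1.0 cc would also double the volume now ordered for donors. This argues for sponsor confirmation before any change.
- **Appendices G, H and I were not supplied.** They may state a dispensing volume. Even so, Sections 3-A and 6.2 would still disagree in the protocol body.
- **The consequence is limited.** The trial is a single-arm feasibility study with no dose comparison. If one volume is used throughout, the longitudinal CTL analysis remains valid for that dose. Lots are labelled with volume and concentration, so the amount given can be worked out later. All of this is fair, but a label that allows reconstruction afterwards does not tell staff which dose to give.

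**Conclusion.** The concern holds. This is an inconsistency between sections in the dose of the investigational product, by a factor of exactly 2: 0.25 mg under Section 6.2 against 0.5 mg under Section 3-A per donor injection.

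The conclusion assumes that the 0.5 mg/ml concentration is correct and that 0.5 mg is the amount per injection. Confidence is high that the two sections conflict. It is lower on which one is wrong, although the vial fill favours 1.0 ml. A twofold difference between donor and recipient is conditional, because Section 6.7 gives no recipient volume. The documents do not show how halving the dose affects immune response, and no safety hazard is claimed. The correction is needed because the dose instruction for the intervention behind the primary aim must be unambiguous.

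**What to change.** The sponsor should first check the intended dose against the manufacturing appendices and the vial label, then correct one section.

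- **If 0.5 mg is intended**, which the vial fill favours: change Section 6.2 to 1.0 cc (0.5 mg idiotype protein).
- **If 0.5 cc is intended**: correct Section 3-A, either the dose to 0.25 mg of idiotype protein (0.5 mg counting KLH) or, if the product really is that strong, the concentration to 1.0 mg/ml.

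In either case, state volume and milligrams of idiotype protein together in Sections 6.2 and 6.7, so that donor and recipient doses are both explicit.

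The cost is a text amendment and a check against the appendices and label. No extra patients or procedures are needed.

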**B. Recipient:**

**Within 10 days prior to lymphocyte infusion and within 72 hours prior to each vaccine:**

- 1) H&P, vital signs.
- 2) Albumin, total protein, calcium, glucose, BUN, creatinine, bilirubin, ALT, alkaline phosphatase, LDH, CBC with differential, PT/PTT.
- 3) GVHD assessment.
- 4) Immunodeficiency panel.
- 5) Negative serum pregnancy test if of child bearing potential.
- 6) Disease specific assessment:
  - SPEP, UPEP, serum and immunofixation electrophoresis, serum for free kappa and lambda light chain assay, Beta 2 Microglobulin, and C reactive protein.

- 7) Collect 10 cc serum and 60 cc peripheral blood in preservative-free heparin for idiotype-specific antibody and cellular proliferative responses, immediately prior to donor lymphocyte infusion, 1 hour after the donor lymphocyte infusion.
- 8) Idiotype-specific humoral and cellular responses will be assessed in both donor and in the recipient post-transplantation.
- 9) Negative donor infectious disease panel:
  - Hepatitis B surface antigen (HBsAg)
  - Anti-Hepatitis B core antibody (HBcAb)
  - Anti-Hepatitis C Virus antibody (HCV Ab)
  - Anti-Human Immunodeficiency Virus (HIV) antibody (HIV 1/2 type O Ab)
  - Anti-Human T cell lymphotropic Virus (HTLV) antibody (HTLV I/II Ab)
  - Rapid Plasma Reagen (RPR)
  - Cytomegalovirus antibody (CMV)
  - HCV/HIV Nucleic Acid Test
  - West Nile Virus Nucleic Acid Test
  - Sickledex
  - T Cruzi AB

Additional tests shall be performed as required to assess the possibility of transmission of other infectious or non-infectious diseases.

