## **9.0 Criteria for Removal from the Study**

1. Patient/Donor withdrawal of informed consent
2. Patient death
3. Disease progression requiring anti-myeloma therapy
4. Patient/ Donor not being compliant
5. 5 years post donor lymphocyte infusion
6. If the recipient does not meet the "pre-vaccine" criteria in Section 7.0 B., the recipient and donor will be taken off the study.
7. Donor lymphocyte collection failure
8. An increasing or unexpected pattern of toxicity observed deemed unacceptable by the study chairman
9. Investigator judgment when the well being and best interest of the patient is compromised.
10. Inability of donor to provide lymphocytes after study registration

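### Section 6.4 states the recipient's tacrolimus and cyclosporine ceilings in ng/dl, probably in place of ng/ml, which makes a mandatory pre-vaccine limit 100 times stricter than it seems meant to be

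*Combined protocol and SAP*

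**What the plan says.** Section 6.4 (6.0 Treatment Plan) lists conditions that the recipient must meet before vaccination. One bullet combines a steroid limit, "On a prednisone or prednisone equivalent dose of no more than 10 mg every other day at the time of registration", with a limit on calcineurin inhibitors, "with tacrolimus levels of <5 ng/dl or cyclosporine levels of < 100 ng/dl". The next bullet reads "Have no uncontrolled GVHD".

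The consequence follows in the same section: "If the recipient does not meet the above 'pre-vaccine' criteria, the recipient and donor will be taken off the study".

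Section 5.0 says that its listed tests "are performed to determine recipient and donor eligibility", and the recipient list in 5.0 B includes "Cyclosporine or tacrolimus level as appropriate". No other section restates the ceilings, and none gives them in ng/ml.

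Section 9.0 item 6 repeats the removal rule but sends the reader elsewhere: "If the recipient does not meet the 'pre-vaccine' criteria in Section 7.0 B". The list in 7.0 B, headed "Within 10 days prior to lymphocyte infusion and within 72 hours prior to each vaccine", contains no drug level and no drug ceiling.

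**The concern.** A decilitre is 100 ml, so the printed ceilings are very low in per-millilitre terms. They sit beside provisions that accept some continuing immunosuppression, and this makes the unit look like a slip for ng/ml.

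The bullet is a decision threshold, not background text. If the unit is wrong, staff have two courses and both are unsatisfactory. Those who follow the text remove recipients, and with them their donors, whom the plan seems to want treated. Those who mentally substitute ng/ml treat these pairs, but against the written criterion. In a trial of at most 10 treated patients, each with an individually made vaccine, either outcome is worth avoiding when one line prevents it.

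**Working it through.** **Inputs.** From 6.4: tacrolimus below 5 ng/dl; cyclosporine below 100 ng/dl. Conversion: 1 dl = 100 ml. The plan derives no figure here, so there is none to reproduce.

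**Conversion.** Limit in ng/ml = limit in ng/dl ÷ 100.

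- Tacrolimus: 5 ÷ 100 = 0.05 ng/ml.
- Cyclosporine: 100 ÷ 100 = 1 ng/ml.

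**How to read the *or*.** Section 5.0 B orders a level of one drug or the other, as appropriate, so the recipient is measured on the drug taken. Section 6.4 uses the same construction. The natural reading is that each ceiling applies to the drug in use.

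**Decision by level, for the drug in use.** The last column assumes that ng/ml was meant.

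| Drug in use | Level (ng/ml) | Limit as printed | Same number in ng/ml |
|---|---|---|---|
| Tacrolimus | below 0.05 | meets | meets |
| Tacrolimus | 0.05 to below 5 | fails | meets |
| Tacrolimus | 5 or more | fails | fails |
| Cyclosporine | below 1 | meets | meets |
| Cyclosporine | 1 to below 100 | fails | meets |
| Cyclosporine | 100 or more | fails | fails |

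The two units give opposite decisions only in the middle band for each drug. Each band spans a factor of 100 (5 ÷ 0.05 = 100; 100 ÷ 1 = 100).

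**Evidence on intent, from the documents only.**

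- Each drug has its own non-zero ceiling. A plan that wanted recipients off both drugs could have said so.
- The same bullet accepts low-dose alternate-day prednisone.
- Only uncontrolled GVHD is a bar, so controlled GVHD is acceptable.
- A drug level is ordered at pretreatment evaluation, so some recipients are expected to be on one of the drugs.

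Together these point to tolerated low-level immunosuppression. None of them states a unit.

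**Cross-reference.** The criteria that 6.4 itself labels pre-vaccine are those listed there. Section 9.0 item 6 names 7.0 B, where this threshold does not appear. This needs no inference, but it is a separate slip and adds no evidence about the unit.

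**The case against.** The strongest reply is that the unit error is not demonstrated. The documents give no assay range, reporting unit, on-treatment level or ng/ml value, and near-undetectable levels might have been wanted. The cues listed above show that some immunosuppression was tolerated, not how much. This stands: the point is a probable error that the investigator must confirm, and the correction has to allow for either answer.

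A second reply is that the consequences are small and unquantified. The number of recipients still on either drug is not given, and no endpoint, sample size, stopping boundary or analysis is touched. This also stands and limits the severity.

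Two stronger readings are tempting. First, a reader might infer that the *or* empties the criterion: someone on tacrolimus alone has no cyclosporine, satisfies that limb, and so passes at any tacrolimus level. That is the result of strict logic, but the wording in 5.0 B supports the drug-in-use reading, under which the drug is capped. The problem is then an over-strict cap, not a missing one. Second, a reader might infer that pairs will be lost after the donor has been vaccinated. The only scheduled drug level is at pretreatment evaluation, whose tests serve eligibility, so a late loss is possible but not shown.

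**Conclusion.** The concern holds as a probable unit error in a mandatory criterion. As printed, the ceilings are 0.05 ng/ml for tacrolimus and 1 ng/ml for cyclosporine, 100 times below what ng/ml would give. The conversion is exact; that ng/ml was intended is a well-supported inference.

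If the inference is right and each limit applies to the drug in use, the text wrongly excludes recipients in the two middle bands, tacrolimus 0.05 to below 5 ng/ml and cyclosporine 1 to below 100 ng/ml. If staff work in ng/ml regardless, those recipients are treated as paper deviations. How many recipients fall in these bands cannot be derived from the documents, and it would be too much to say that every recipient on either drug fails: that needs an assumed on-treatment level that the plan does not supply. Severity is minor.

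**What to change.** Ask the investigator to confirm the unit. If ng/ml was meant, replace the limit in 6.4 with: *tacrolimus <5 ng/ml if on tacrolimus; cyclosporine <100 ng/ml if on cyclosporine*. If near-zero levels are truly intended, write instead: *off tacrolimus and cyclosporine*. Either wording also settles how the *or* is to be read.

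As a side correction, change the pointer in 9.0 item 6 from Section 7.0 B to Section 6.4.

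The cost is one query, one line and one cross-reference. Correcting the unit requires no new test, since 5.0 B already orders the level, and no change to the timing of checks or to Section 10.0.
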